- **Cincinnati** - Cincinnati Children's Hospital Medical Center
- **Aurora** – University of Colorado SOM and Children's Hospital Colorado
- **Houston** – Baylor Medical College and Texas Children's Hospital
- **Indianapolis** – University of Indiana and Riley Hospital for Children
- **Minneapolis** – University of Minnesota
- **Seattle** – University of Washington and Seattle Children's Hospital
- **St Louis** - Washington University and St Louis Children's Hospital
- **Toronto** - The Hospital for Sick Children and University of Toronto

Fibroscan is available through the NIH at the bolded centers. Baltimore and Minneapolis and St Louis do not have Fibroscan available at this time. If it becomes available, they will participate in this study.

The CFLD NET study is supported by the ChiLDReN Data Coordinating Center (DCC) at the University of Michigan/Arbor Research and the clinical component is funded by the CF Foundation

Study Aims and Hypotheses

- Primary Objective:
- Aim 1:
 - To determine if transient elastography (TE), when combined with ultrasound (US) pattern characterization can improve the prediction of progression to a nodular pattern on US.
 - - o Hypothesis 1: TE results can differentiate children with a heterogeneous or homogeneous patterns on grayscale liver US who will progress to a nodular pattern on US
- Secondary Objectives
- Aim 2: To confirm the feasibility of obtaining TE measurements in children with CF
 - o Hypothesis 2a: Valid TE measurements will be obtained in more than 90% of children with CF
 - o Hypothesis 2b: To determine the variability of TE measurements taken at different liver sites in the same patient
- Aim 3: To prospectively assess whether TE data are associated with conventional markers of hepatic fibrosis and portal hypertension
 - o Hypothesis 3: TE based values will correlate with conventional biomarkers of fibrosis/liver disease severity in CF: APRI, Fib-4, platelet count and spleen size
- Exploratory Objectives:
- Aim 4: To determine if TE with fat content can improve assignment of grade in situations where there is a dichotomy of radiology grades (i.e. 2 HTG, 2NL)

August 12, 2016

- Hypothesis 4a: The combination of grayscale liver US image pattern assessment and TE values with fat content will differentiate between those individuals with dichotomous radiology grades (2HTG/2NL 2HTG/2HMG or 2HTG/2CIR) and risk of progression to a nodular pattern on US.

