The estimated 2-4 year progression rate is ~40% in HTG subjects. Thus of the 33 available with HTG pattern, 10-13 would be predicted to progress to CIR. However, as the study is in progress, ~20% have progressed so the risk of progression may be lower. We choose to make a conservative assumption in our power calculation: 20% of HTG subjects will progress to CIR pattern, and 2% of NL or HMG subjects will progress to CIR pattern. In addition, we assume the liver stiffness measure follow a lognormal distribution with location =0 and scale parameter =0.5 (i.e. median=1, Q1=0.71, Q2=1.4). With 142 subjects (approximately 63% NLs, 23% HTGs, and 13% HMGs) we will have 80% power to detect an odds ratio of 4 for a 1 unit increase in the liver stiffness measure. (Caveat: Given that we do not have any preliminary data of TE measures in CF subjects, the results of this power calculation only give us a general guidance).

Hypothesis 2a: Valid TE measurements will be obtained in more than 90% of children with CF

Analysis:

For hypothesis 2a, we will estimate the proportion of subjects in whom a valid transient elastography measurement can be obtained. At each site, all measurements will be performed by one of the trained examiners. The results will be reported as the median of 10 valid measurements and will be accepted as valid if the ratio of the interquartile range (IQR) and median was < 30% and the success rate was > 60% (8, 9). Per Goldschmidt 2013 (9) we will define two measures of the feasibility of transient in our population: “technically possible” and “acceptable quality.” The proportion of subjects with a “technically possible” FibroScan™ is defined as the number of subjects with at least 10 FibroScan™ measurements obtained divided by the number assessed. The proportion of subjects with FibroScans™ of “acceptable quality” is defined as the number of subjects with FibroScan™s with the ratio of the interquartile range and median of the 10 measurements <30%, divided by the number assessed. The proportions and their 95% confidence intervals will be provided using the Wald method. We will do a stratified (separate) analysis by <8 years of age and >8 years of age. There will be the opportunity to compare this data to children with other liver diseases in the ChiLDReN FORCE study.

Hypothesis 2b: To determine the variability of TE measurements taken at different liver sites in the same patient

Analysis

August 12, 2016

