Variability of TE measurements at a single liver site will be quantified by the ratio of the interquartile range and the median (RIM). Absolute difference in RIM between the two liver measuring sites in the same patient will be calculated. Distribution of this absolute difference will be studied using kernel density estimation to identify whether the distribution has more than one mode (whether these are heterogeneous groups according to difference in variabilities between sites in the same patient). We will also study whether this RIM is associated with the median of the stiffness measurements in the same patient.

Hypothesis 3: TE based values will correlate with conventional biomarkers of fibrosis/liver disease severity in CF: APRI, Fib-4, platelet count and spleen size

Analysis: Graphic method will be used to explore relationship between TE based values and conventional biomarkers. Pearson or Spearman correlation will be calculated.

Exploratory analyses:

Hypothesis 4a: The combination of grayscale liver US image pattern assessment and TE values with fat content will differentiate between those individuals with dichotomous radiology grades (2HTG/2NL 2HTG/2HMG or 2HTG/2CIR) and risk of progression to cirrhosis.

Analysis:

ANOVA or Kruskal-Wallis test, whichever is appropriate, will be used to compare TE measures between the three groups.

Hypothesis 4b: Higher fat content will be associated with a lower risk of progression to cirrhosis

To test whether subjects with a high TE determination of fat content and heterogeneous pattern on US will not progress to an US pattern of cirrhosis (Hypothesis 5b), we will add the TE measure of fat content to the second model for testing hypothesis 1 (i.e. this model will include three predictors: grayscale US, liver stiffness, and fat content). The hypothesis can be tested through testing the regression coefficient for the fat content variable. A significant negative regression coefficient will support our hypothesis. All subjects graded as NL, HMG, or HTG at the time this ancillary study starts will be included in the analysis.

Hypothesis 5: Among those children with a nodular pattern on US, TE results will correlate with clinical findings of portal hypertension (splenomegaly, thrombocytopenia, variceal hemorrhage and/or ascites)

Analysis:

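### The three-group comparison planned for exploratory Hypothesis 4a tests neither grade assignment within a split reading nor progression in split-grade children

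*Protocol*

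**What the plan says.** Aim 4 (Study Aims and Hypotheses, exploratory objectives) is "To determine if TE with fat content can improve assignment of grade in situations where there is a dichotomy of radiology grades". Hypothesis 4a, as repeated in the statistical section, says that the combination of grayscale US pattern and TE values with fat content "will differentiate between those individuals with dichotomous radiology grades (2HTG/2NL 2HTG/2HMG or 2HTG/2CIR) and risk of progression to cirrhosis".

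The whole analysis given for 4a is one sentence: "ANOVA or Kruskal-Wallis test, whichever is appropriate, will be used to compare TE measures between the three groups".

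Hypothesis 4b is listed under the same aim. For it, "we will add the TE measure of fat content to the second model for testing hypothesis 1", which gives a progression model with US grade, stiffness and fat content as predictors. Its population is stated as: "All subjects graded as NL, HMG, or HTG at the time this ancillary study starts will be included in the analysis".

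The protocol gives no number of split readings and no power statement for 4a.

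**The concern.** Aim 4 asks a question within each split: given that two readers say HTG and two say something else, do stiffness and fat content point to the right one? Hypothesis 4a adds whether these children go on to progress. The planned test works between splits. Its grouping variable is the type of split, which is already known from the readings. It uses no reference for the correct grade, no progression outcome, and no joint use of US, stiffness and CAP.

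At stake is how the result would be read. A significant test could be reported as evidence that TE helps with disputed grades or with prognosis when it shows only that the types of split differ. A null result could be taken as evidence against a useful marker. This is not a detail left for the SAP: the protocol names a test, and the test does not match the hypothesis.

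**Working it through.** The protocol gives no figure for 4a to reproduce, so the check is first of logic and then by illustration.

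**Question against test**

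| Element of Aim 4 / Hypothesis 4a | In the 4a test? | In the 4b model? |
|---|---|---|
| TE differs among the three split types | Yes | No |
| Which of the two competing grades applies within a split | No | No |
| Risk of progression | No | Yes, in all NL/HMG/HTG subjects |
| Progression in split-grade children specifically | No | No split-reading term |
| US, stiffness and CAP used jointly | No | Yes |

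**Illustration.** Each setting has 4,000 simulated trials, tested at 5%. Group sizes and shifts are assumptions.

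*(a) TE uninformative within splits.* Three normal groups have means 0, 0 and 1 SD, and TE is unrelated to which grade is correct. ANOVA rejects in about 28% of trials at 5 per group, 46-48% at 8 and 66-68% at 12. Kruskal-Wallis is slightly lower, at about 24%, 42% and 64%.

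*(b) TE uninformative on progression, larger shift.* From Power calculations under Hypothesis 1: "we assume the liver stiffness measure follow a lognormal distribution with location =0 and scale parameter =0.5". Progression is set at 20%, the protocol's HTG assumption ("20% of HTG subjects will progress to CIR pattern"). One split type is shifted by 1.0 on the log scale, which is 1.0/0.5 = 2 SD, and progression is independent of TE. The AUROC within splits is about 0.50. Kruskal-Wallis rejects in 77% and ANOVA on log TE in 83% at 5 per group; both reject in 99% or more at 10 and in 100% at 20.

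*(c) TE predicts progression equally within every split type.* The distribution and the 20% rate are as in (b), but the 1.0 log shift now applies to progressors in all three types. The expected AUROC within splits is Φ(1.0 / (0.5 × √2)) = Φ(1.414) = 0.92, and the simulation gives 0.92. Kruskal-Wallis rejects in 4.4% to 4.7% and ANOVA in 4.7% to 5.4% at 5, 10 and 20 per group. This is the false-positive rate, because the three groups have the same TE distribution.

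The test can therefore be positive when TE predicts nothing within splits, and it is uninformative when TE predicts progression well in every split type.

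*(d) TE resolves every split.* Each group is a 50:50 mixture of true HTG (mean 0) and its alternative: −2 SD for NL and for HMG, +2 SD for CIR. The three-group Kruskal-Wallis rejects in about 44-45%, 72-73% and 90-91% of trials at 5, 8 and 12 per group. The planned test does respond here, but because the 2HTG/2CIR group sits higher on average, not because any split has been resolved. Restricted to 2HTG/2NL against 2HTG/2HMG, it rejects in about 5%.

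**The case against.** Four points on the other side have force.

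- **Literal wording.** If differentiating between those individuals means only that TE differs among the listed split types, the test addresses the first half of 4a. That stands. It leaves the progression half untested and does not meet Aim 4's stated purpose of grade assignment.
- **Hypothesis 4b.** A reader might infer that Aim 4 cannot be answered at all. The protocol does not support that. The 4b model relates US grade, stiffness and fat content to progression, and it includes split-grade children whose grade is NL, HMG or HTG. What it lacks is any term for a split reading, and it does not address grade assignment.
- **A null result when TE resolves every split.** This stronger claim is tempting, but it holds only if the 2HTG/2CIR group is left out. With all three planned groups, the test rejects often in that situation (setting d).
- **Fat content.** A reader might infer that CAP is ignored. The FibroScan section lists stiffness and CAP as the two measured parameters, so the plural "TE measures" in the 4a analysis can cover both. They are still not combined.

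It is also fair that the aim is exploratory, carries no power claim and does not bear on the primary objective. This limits the weight of the point but does not make the test fit the question.

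**Conclusion.** The mismatch holds. The only analysis stated for Hypothesis 4a can show that TE differs by type of split reading. It cannot test whether TE with fat content tells which grade applies within a split, or whether it predicts progression in split-grade children. Hypothesis 4b fills the progression gap in part, for NL/HMG/HTG subjects as a whole.

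The rejection rates rest on assumed group sizes (5 to 20) and assumed shifts (1 or 2 SD), since the protocol does not say how many split readings exist. The conclusion does not depend on them, because it follows from the outcome and reference grade being absent from the test. The point is worth correcting but is confined to an exploratory aim.

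**What to change.** Keep the three-group comparison, labelled as descriptive, and add two analyses.

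1. **Progression.** Use the existing Hypothesis 1/4b discrete-time logistic model (US grade, stiffness, CAP) with a split-reading indicator and, if events allow, its interaction with TE. Use penalised estimation, and report estimates with confidence intervals for split-grade children with an NL, HMG or HTG consensus. A separate model in split-grade children alone is not advisable. With 5 to 12 in each of 2HTG/2NL and 2HTG/2HMG there would be 10 to 24 children, and at 20% progression only about 2 to 5 events (10 × 0.20 = 2; 24 × 0.20 = 4.8).
2. **Grade assignment.** Derive a stiffness-plus-CAP score in children with undisputed grades and apply it to split-grade children. Report it descriptively against the later consensus US grade. State that research US is done every 2 years, so a later change may be true progression rather than correction of the first grade.

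The alternative is to narrow Aim 4 and Hypothesis 4a to the descriptive comparison.

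The cost is analysis wording. TE, CAP and follow-up US are already scheduled, and the 2:2 notation implies that individual reader grades exist. The downside is imprecision, because split-grade children and progression events will be few.

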- “Controlled Attenuation Parameter (CAP)” quantifies liver steatosis and is measured in dB/m (median of 10 subsequent valid measurements).

In addition quality control data are collected:

- Invalid measurements and success rate
- Number and list of valid measurements
- Inter quartile range (IQR) (kPa or dB/m) of all valid measurements within the examination (reflects the dispersion of stiffness or CAP measurements)
- IQR/med. (%) Indicates the IQR/median ratio and should remain as low as possible to ensure reliable results (goal < 30%)

Study withdrawal/discontinuation

The participant and/or participant’s family may withdraw from the study at any time. The study investigator can withdraw the participant from the study at any time if that is felt to be in the best interest of the participant and/or their family. If a participant in the longitudinal follow up study meets an endpoint for the end of the PUSH study (liver transplantation or death) they will have met the end of this study.

Statistical and Design Considerations

Based upon interest and involvement of the subjects in PUSH, we anticipate all subjects currently available (168) will enroll. If TE becomes available at the 3 centers without TE, then up to an additional 60 subjects would be available to enroll. TE would be available from all eligible US pattern subjects.

Hypothesis 1: TE results can differentiate children with a heterogeneous or homogeneous pattern on grayscale liver US who will progress to a nodular pattern on US

Analysis:

To test whether TE, when combined with US pattern characterization can improve the prediction of progression to a nodular pattern on US, we will build two discrete survival models using logistic regression. In the first model, greyscale US consensus grade will be used to predict prediction to nodular pattern. In the second model, we will add the predictor liver stiffness measured by TE. If the second model significantly increases the area under the receiver operating characteristic curve

August 12, 2016

(AUROC) comparing to the first model, we will conclude that TE can improve the prediction of progression to a nodular pattern on US. All subjects graded as NL, HMG, or HTG at the time this ancillary study starts will be included in the analysis.

Power calculations:

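### Hypothesis 4b fits three predictors to about 9 expected events by ordinary logistic regression, and its sentence about heterogeneous-pattern children does not match the pooled coefficient it tests

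*Protocol*

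**What the plan says.** The second Hypothesis 1 model predicts progression to a nodular pattern from ultrasound grade and liver stiffness. It is one of "two discrete survival models using logistic regression" (Protocol, Statistical and Design Considerations, Hypothesis 1, Analysis). Hypothesis 4b adds fat content: "this model will include three predictors: grayscale US, liver stiffness, and fat content" (Exploratory analyses, Hypothesis 4b). The decision rule is "A significant negative regression coefficient will support our hypothesis", and the analysis set is "All subjects graded as NL, HMG, or HTG at the time this ancillary study starts will be included in the analysis". No small-sample method is named.

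Two statements of the claim stand together in that section. The heading is general: "Higher fat content will be associated with a lower risk of progression to cirrhosis". The sentence introducing the test is narrower and stronger: it is to show that "subjects with a high TE determination of fat content and heterogeneous pattern on US will not progress". That sentence also labels itself Hypothesis 5b, although it stands under 4b.

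The rates come from the Hypothesis 1 power calculation: "20% of HTG subjects will progress to CIR pattern, and 2% of NL or HMG subjects will progress to CIR pattern". The same paragraph first gives a higher figure: "The estimated 2-4 year progression rate is ~40% in HTG subjects". No event count, fat-content distribution, effect size or power is given for 4b.

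**The concern.** There are two separate issues.

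**Estimation.** With few events per coefficient, maximum-likelihood log odds ratios lie on average too far from zero when a true effect exists. A grade in which nobody progresses has no finite coefficient. A protective effect of fat content, if real, would tend to be reported as larger than it is.

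**Population.** The sentence introducing the test concerns HTG children, but the quantity tested is one main effect over NL, HMG and HTG, with no grade-by-fat term and no HTG-only estimate. A pooled result could be reported as a finding about HTG children.

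**Working it through.** **Inputs from the protocol.** 90 NL, 33 HTG and 19 HMG at centers with TE (142 in all); progression 20% in HTG and 2% in NL or HMG; lognormal(0, 0.5) stiffness; odds ratio 4 per unit of stiffness; 90% TE success (Recruitment, enrollment and follow-up). The two-sided 5% level is stated only for Hypothesis 5 and is assumed here.

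**The plan's own figure.** The 80% power for Hypothesis 1 is reproduced by simulation with a grade-adjusted likelihood-ratio test. Power is 79.5% or 81.2% if 20% and 2% are the risks at mean or median stiffness (10.7 or 12.4 events). It is 71.5% if they are the overall rates in each group (8.8 events). The overall reading is used below.

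**Expected events.**
- HTG: 33 × 0.20 = 6.6. NL and HMG: 109 × 0.02 = 2.2. Total 8.8, of which 75% are in HTG.
- With 90% TE success: 8.8 × 0.9 = 7.9.
- With 40% progression in HTG: 33 × 0.40 + 2.2 = 15.4.
- Events per predictor: 8.8 / 3 = 2.9. With grade as three categories there are four slopes: 8.8 / 4 = 2.2.

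**Chance of a grade without events.** HMG: 0.98^19 = 0.68. NL: 0.98^90 = 0.16. At least one of the two: 1 − (1 − 0.16)(1 − 0.68) = 0.73. The affected grade coefficient is then not finite, but the fat coefficient stays estimable.

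**Bias of the fat coefficient.** There were 2,000 simulated studies per setting, with one record per child, standard-normal fat content (assumed), and stiffness odds ratio 2 / 4. Entries are log odds ratios per SD of fat content.

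| True value | ML mean | ML median | Firth mean |
|---|---|---|---|
| 0 | −0.01 / −0.01 | −0.01 / −0.01 | −0.01 / −0.01 |
| −0.40 | −0.47 / −0.48 | −0.43 / −0.43 | −0.40 / −0.39 |
| −0.69 | −0.84 / −0.88 | −0.78 / −0.74 | −0.70 / −0.68 |
| −1.11 | −1.43 / −1.49 | −1.23 / −1.21 | −1.12 / −1.10 |

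The mean excess is 18-26% in the middle two rows and 29-34% in the last, where a few extreme estimates pull the mean. With extremes trimmed it is 14-20% across the three rows with an effect. The median excess is 7-12%. Further runs at stiffness odds ratio 4 gave ML means of −0.79 for a true −0.69 (14%) and −1.25 for a true −1.05 (19%). Firth means there were −0.68 and −1.05, with 16-27% lower root mean square error. At 15.4 events the ML mean is −0.79 for a true −0.69, also 14%.

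**Test.** With no fat effect, ML rejects in 3.2-4.0% of studies (Wald) and 5.1-6.1% (likelihood ratio). Firth rejects in about 3-4%. Power at odds ratio 0.5 per SD is 40-45% (ML likelihood ratio).

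**Effect confined to HTG.** With a true HTG log odds ratio of −0.69 and none elsewhere, the pooled ML coefficient averages −0.60 (median −0.52).

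**The case against.** The strongest reply is that the rule looks at sign and significance, not size, and the ML type I error of about 3-6% gives no sign that it misleads. That stands. A reader might infer that the test is invalid, and the calculations do not support it.

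A reader might also infer that the protective effect will necessarily be overstated. It need not be. The bias is an average tendency, absent under no effect and smaller in the median. In one set of runs at a true odds ratio of 0.5, only 55% of estimates fell beyond the true value. The two issues can also pull in opposite directions: if fat content acts only in HTG, pooling moves the coefficient toward zero.

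The 73% chance of an empty grade might suggest that the fat test breaks down. It does not. Merging NL with HMG barely changed the fat coefficient (mean −0.82 to −0.81, power 41% both ways), so merging is not needed for 4b. The protocol also does not say how grade is coded, so four slopes is an assumption.

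On population, the pooled model does answer the general heading, it adjusts for grade, and 75% of expected events are in HTG. With its stale label, the narrower sentence may be leftover wording. This limits the issue to reconciling one sentence with the analysis set.

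Finally, 4b is exploratory, and an analysis plan not seen here may name an estimator. But the protocol itself fixes the model, the rule and the analysis set, and its rates imply very few events. A less biased estimator with smaller error is available at almost no cost.

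**Conclusion.** The point holds as a minor one. At the protocol's conservative rates, about 9 events support a three-predictor model, or about 15 if 40% of HTG children progress. If fat content has a real effect, the ordinary coefficient is on average about 15-25% too far from zero and roughly 10% in the median. There is no bias under no effect, and type I error is not materially wrong. A grade coefficient (NL or HMG) would have no finite estimate in about 73% of studies if grade has three categories.

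The sentence about heterogeneous-pattern children does not match the heading, the analysis set or the coefficient. If the effect is confined to HTG, the pooled coefficient understates it (about −0.6 against −0.69).

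The bias figures rest on assumed standard-normal fat content, assumed fat odds ratios of 0.33 to 0.67 per SD and one record per child instead of person-period records. The event count and the empty-grade probability follow from the protocol's own numbers.

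**What to change.** - Fit the 4b model by Firth penalised likelihood, with a profile-likelihood confidence interval and a penalised likelihood-ratio test for the fat coefficient.
- Report that coefficient as a grade-adjusted association over NL, HMG and HTG together.
- Reword the sentence introducing the test to match the heading: lower risk, no restriction to HTG, and the label 4b.
- Give an HTG-only Firth estimate beside it, labelled descriptive, since it rests on about 7 events.

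The cost is a software option and a few words of text. Estimates will be less extreme, and power slightly lower than with the ML likelihood-ratio test. Low power is not cured, so a non-significant result should not be read as evidence that fat content is unrelated to progression. Nor does Firth estimation correct for pooling if the effect is confined to HTG. That is why the HTG-only estimate is shown.
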